**What data will be collected and how:**

- Participant responses to the symptom reporting questions within eSyM will be collected.
- Patient and clinician eSyM usage reports will be collected.
- Patient-reported self-efficacy, attainment of information needs, symptom burden, and satisfaction with care will be collected via the SASS Questionnaire.
- Patient feedback on the eSyM program and experiences with care team and symptom management via qualitative interviews.
- Study-related health information and outcomes will be collected via medical record (and/or local cancer registry) review (automated and manual).
- Hospital/clinic characteristics will be collected.
- All data collected for this study will be submitted to the coordinating center (Dana-Farber Cancer Institute).

**Long-term follow-up:** The patient's medical record may be reviewed for outcomes for up to 1-year after the trigger event (i.e., new chemotherapy treatment plan and/or surgery).

**Activity 5: Integration of eSyM data to develop algorithms to estimate outcomes, including the risk of ED usage and hospitalization, among patients with suspected or confirmed cancer**

**Brief description of activity:** Patients receiving treatment for metastatic cancer have high symptom burdens and high rates of adverse events, including emergency department (ED) use and hospital admissions, which can impact patients' quality of life. Some of these adverse events may be preventable if providers can match patients with appropriate outpatient services. However, to achieve this goal, we must improve our ability to prospectively identify the patients

at increased risk for near-term adverse events and most likely to benefit from intensification of outpatient care.

Several studies have used EHR data to predict risk of death in cancer patients. However, efforts to date have several limitations. They rely on computationally-intensive methods that are difficult to implement in routine clinical practice. Little work has been done to develop models that predict adverse events which are actionable in the near-term. Existing risk-prediction models are susceptible to racial biases; little research has evaluated whether these models' calibrations may have racial biases. And few efforts have incorporated newer data sources, such as ePROs, into risk prediction models. ePROs, which are now frequently collected in routine clinical care, may improve predictions.

We aim to develop methods to predict which patients are at the highest risk for undesirable outcomes, including hospitalization and ED use. These predictions will lay the foundation for future work to develop targeted interventions to intensify outpatient care and reduce preventable adverse events. Specifically, we will use SIMPRO data (including demographics, conditions, medications, encounters, ePROS, etc.) to develop predictive models that are built using machine learning clinical risk prediction techniques. Through these efforts, we seek to address a number of important questions, including how ePRO data affect model performance; how clinical risk scores perform relative machine learning algorithms; and whether there are differences in model performance among different patient subgroups (to determine whether predictive model calibrations based on EHR data may be intrinsically biased).

Using data from six health systems will allow us to evaluate algorithms to predict adverse events in diverse clinical settings

**Specific Aims:**

1. Develop algorithms to estimate the risk of adverse events, including ED usage and hospitalization, among patients with suspected or confirmed cancer who are treated in community settings.
2. Assess whether inclusion of ePROs improves algorithm performance and how predictions from clinical risk scores compare to predictions from computationally intensive machine learning approaches
3. Assess model performance among historically under-represented populations, including Black patients, and assess for evidence of racial bias in model calibration.

**Human Subjects Research Category (NHSR, exempt, expedited, full review):** Exempt

**Informed Consent:** Waiver of consent (retrospective data review).

**Activity 5 Population:** All patient-level data collected in Activity 4 will be utilized. To date, the SIMPRO consortium has collected more than 50,000 survey responses and EHR data for more than 13,000 medical oncology and surgical oncology patients across these systems. These data

present an opportunity to develop and test algorithms to predict adverse events in patients receiving care for a suspected or confirmed cancer.

**Number of subjects (per site and overall):** All patient-level data collected in Activity 4 will be utilized.

**When, where, and how potential subjects will be recruited:** Not applicable. Only previously collected patient-level data will be utilized.

**Materials that will be used to recruit subjects:** Not applicable. Only previously collected patient-level data will be utilized.

**Duration of subject's participation in the study:** Not applicable.

**Duration anticipated to enroll all study subjects:** Not applicable.

**Study design:** Retrospective data analysis project.

**Description of all research procedures being performed:** We will use data previously collected for the SIMPRO project to develop and evaluate the performance of predictive models for adverse events among patients with suspected or confirmed malignancy. The only new procedures will include novel analyses of existing data.

**Monitor subjects for safety or minimize risks:** Not applicable, only deidentified datasets will be utilized for predictive modeling work.

**What data will be collected and how:** Not applicable, previously collected data will be utilized.

**Long-term follow-up:** Not applicable.

## 6.0 Study-Wide Number of Subjects

Activity 1 – Stakeholder Engagement				Activity 2	Activity 3- Patient Engagement	Activity 4 - Patient Engagement	Activity 5 – Predictive Modeling Algorithms
Patient Advisory Council	Health system leaders	Clinicians and staff	Follow- up	Build eSyM	UAT/Pilot study	Pragmatic stepped- wedge cluster randomized trial	Integration of eSyM data
	Exempt, waiver of consent				NHSR	3a) NHSR 3b) Waiver of documentation of consent 3c) Waiver of consent 4d) Written consent	4a) NHSR 4b) Waiver of documentation of consent 4c) Waiver of consent 4d) Written consent
Study- Wide Accrual	30-150 a	24-60 a	360 a	720 a	n/a	390	6,048 ( minimum ) d [1,980 of whom will complete the SASS Questionnaire and 48 patient interviews]
Accrual per site	5-25 a,c	4-10 a,c	60 a,c	120 a,c	n/a	90 c at Dana-Farber, and 60 c at each of the other participating sites.	1,008 c ( minimum ) d at each of the six participating sites [330 of whom will complete the SASS Questionnaire and 8 taking part in patient interviews]
	GRAND TOTAL MAXIMUM ACCRUAL ACROSS ALL STUDY ACTIVITIES PER SITE = 5,000 GRAND TOTAL MAXIMUM ACCRUAL ACROSS ALL STUDY ACTIVITIES STUDY-WIDE = 30,000						

a Number can be larger or smaller depending on meeting attendance and availability of staff.

b Interviews/surveys will continue until thematic saturation is reached.

c Protocol does not mandate equal distribution of participants among participating sites.

d The entire statistical analysis section is predicated on *minimum* N = 6048. Because the goal is broad-based systems-level implementation, we anticipate having much higher N which will enable us to examine effectiveness in subgroups of interest.

## 7.0 Study-Wide Recruitment Methods

Each activity utilizes slightly different recruitment methods. See section 5.0 for details.

## 8.0 Multi-Site Research

This is a multi-site study. The lead site and coordinating center for this protocol is Dana-Farber Cancer Institute. The regulatory sponsors are [name] MD MPH (Co-Grant PI and Study Chair) and [name] MD MPH (Co-Grant PI and Coordinating Center Site PI). **All participating sites are required to adhere to the Data Safety and Monitoring Plan (DSMP) for this study (see Appendix S).**

## 9.0 Study Timelines

The duration of an individual subject's participation in the study and the duration anticipated to enroll all study subjects varies by activity. See section 5.0 for details.

The estimated date for the investigators to complete primary analyses is September 30, 2023. Secondary analyses are estimated to be completed by August 31, 2024. The estimated date of study completion is December 31, 2024. Dates are subject to change.

## 10.0 Study Endpoints and Statistical Analyses

**The detailed protocol statistical analysis plan (SAP) can be found in Appendix TT.**

### Analysis of activity 1 (stakeholder engagement):

Quantitative interviews will be scored using their established scoring metrics:

- The NOMAD instrument is a 23-item survey that measures implementation processes from the perspective of professionals directly involved in the work of implementing complex interventions in healthcare. [Appendix J]
- The AIM (Acceptability of Intervention Measure), IAM (Intervention Appropriateness Measure), and FIM (Feasibility of Intervention Measure) instruments are four-item measures of implementation outcomes that are often considered “leading indicators” of implementation success. [Appendix G]
- The CSAT (Clinical Sustainability Assessment Tool) instrument is a 49-item survey with 7 domains used by evaluators and researchers to determine the extent to which a practice is being implemented effectively. (Appendix Y)
- The ORCA (Organizational Readiness to Change Assessment) instrument is a 74-item survey with three domains, each item has been mapped to a CFIR construct, and will be scored according to Helfrich et al.'s (2009). [Appendix B]
- The OCM (Organizational Change Manager) instrument is a 60-item survey with 15 domains, each item has been mapped to a CFIR construct, and will be scored according to Gustafson et al.'s (2003). [Appendix B2]

Qualitative interviews (audio recordings and notes) will be evaluated for common themes. Results from the qualitative and quantitative interviews and surveys will be used to inform eSyM, its content, its rollout, and the training materials.

Analysis of Activity 3 (UAT/Pilot study):

Study staff will observe patient/proxy, clinician and clinical support staff action steps and interactions with the system. Observations will be recorded and used to refine eSyM, its rollout, and the training materials.

Any patient data collected will be analyzed as per the analysis plan for the stepped-wedge cluster randomized trial described below.

Analysis of Activity 4 (stepped-wedge trial):

*Additional details can be found in Appendix TT. Please reference Appendix TT for the most updated SAP.*

**Study Design:** Type II Hybrid Effectiveness-Implementation Stepped Wedge Cluster Randomized Trial. The research team will partner with software developers at Epic to adapt working ePRO symptom management systems, one in surgical and one in medical oncology, and fully integrate them into the EHR at 6 health systems. After pilot testing, we will conduct a pragmatic stepped wedge cluster randomized trial to measure the effectiveness of the ePRO system on outcomes that matter to patients and clinicians. Throughout, we will evaluate the implementation process to optimize sustainability and generate actionable knowledge that facilitates scaling to other settings. The proposed study is a hybrid effectiveness-implementation type I trial according to the Curran schema. The study meets PRECIS-2 criteria for pragmatic trials based on scores of 4 or higher in each domain. Reports will adhere to the revised Criteria for Reporting the Development and Evaluation of Complex Interventions in healthcare (CReDECI2), the CONSORT PRO and cluster randomized extensions, and the stepped wedge reporting guidelines proposed by Grayling.

The PICOTS FRAMEWORK. 	
Populations	

1) Adult patients with GI, GYN, or Thoracic cancer having a new treatment plan

2) Adult patients with suspected GI, GYN, or thoracic cancer having a priority surgery

 
**Patients were seen at the participating sites between January 1, 2018 and March 31, 2024. Dates are subject to change.**

Intervention	
eSyM: A multi-component ePRO Symptom Management system based on PRO-CTCAE with:
 

1. Patient-facing components:

• Prompts for between-clinic visit symptom reporting and the ability to view profiles over time

• Evidenced-based education for self-management in response to symptom reports

• Alerts to contact the clinical team in response to severe or escalating symptoms

	
2. Clinician-facing components:
 
 
• View patient profiles in EHR flowsheet, accessible between or during visits, easily added to notes
 
• Receive alerts for severe symptoms in the EHR, same as for abnormal lab tests
 
• Dashboard functionality to track symptoms for groups of patients
 

Control	No eSyM symptom reporting
Outcomes	Emergency department visits culminating in discharge, hospitalizations, symptom burden, care satisfaction
Timing	4-year study of surgical and medical oncology patients each followed for up to 1 year after the trigger event (i.e. new chemotherapy treatment plan and/or surgery)
Setting	Six health care systems, all small cancer centers. All use an Epic EHR.
Design	A hybrid Type II effectiveness-implementation pragmatic cluster randomized trial, with stepped wedge rollout (6 steps), patient as the unit of analysis and closed (cross-sectional) cohort design

### **Randomization:**

We will conduct a stepped wedge cluster randomized trial to determine whether ePROs are clinically effective. This stepped wedge design has 6 steps, and we randomize 6 sites (Table) to the steps.

Table: Six participating sites and region

Site	Region
WVU	Southern
Baptist	
Dartmouth	Northern
Maine	
DFCI/BWH/MGH	Urban
Lifespan	

To ensure that two sites with the same attribution will not be assigned to the same rollout step group (early MO/late surgery or late MO/early surgery), we employ a stratified randomization by region. As a result, each of the two groups has a site from each of the three regions (Northern, Southern, and Metropolitan). The stepped wedge design includes seven time-periods, including a run-in period (Figure)..

Figure: Study design

Group	Step	Run-in	Period 1	Period 2	Period 3	Period 4	Period 5	Period 6
Early MO /late surgery group	Step 1		MO	MO	MO	MO	MO	MO
								Surgery
	Step 2		MO	MO	MO	MO	MO	MO
							Surgery	Surgery

	Step 3			MO	MO	MO	MO
				Surgery	Surgery	Surgery	Surgery
	Step 4				MO	MO	MO
				Surgery	Surgery	Surgery	Surgery
	Step 5					MO	MO
			Surgery	Surgery	Surgery	Surgery	Surgery
	Step 6						MO
			Surgery	Surgery	Surgery	Surgery	Surgery

MO: Medical oncology

Surgery: Surgical patients

**The sites were randomized on 11/6/18 as follows:**

Group	Step	Run-in	Period 1	Period 2	Period 3	Period 4	Period 5	Period 6
Early MO /late surgery group	Baptist		MO	MO	MO	MO	MO	MO
								Surgery
	Maine			MO	MO	MO	MO	MO
								Surgery
	Dana-Farber/BWH			MO	MO	MO	MO	MO
						Surgery	Surgery	Surgery
Late MO /early surgery group	Lifespan				MO	MO	MO	MO
				Surgery	Surgery	Surgery	Surgery	Surgery
	Dartmouth						MO	MO
				Surgery	Surgery	Surgery	Surgery	Surgery
	WVU							
			Surgery	Surgery	Surgery	Surgery	Surgery	Surgery

**Analysis of Activity 4d (Patient qualitative interviews):**

Qualitative interviews (audio recordings and notes) will be evaluated for common themes using NVIVO. Results from the qualitative interviews will be used to inform eSyM enhancements, program content, program rollout, and implementation strategies.

**Analysis of Activity 5:**

We will extract structured data from the six health systems participating in SIMPRO. These data include ePROs, demographics, diagnoses, treatment plans, medications, and inpatient and outpatient encounters. We will develop risk prediction models for adverse events, especially including, but not limited to hospitalizations and emergency department visits. Planned hospitalizations will be identified and excluded based on A) admissions within 24 hours of the

triggering surgery among surgical patients; and B) admissions associated with curative-intent surgeries among medical oncology patients with early-stage cancers. For models incorporating ePROs as predictors, the analytic cohort will include patients who completed at least one survey. For models excluding ePROs as predictors, the analytic cohort will include all patients in the database.

Data from at least one health system will be removed from the dataset to serve as an external test set. Among the remaining health systems, the population will be split at the patient level with 70% randomly assigned to a training cohort, 15% assigned a validation cohort and 15% assigned to an internal test set. To account for differences in clinical practice and demographics across health systems, randomization will be stratified by system. The same cohorts will be used to train and test all algorithms.

To determine the optimal machine learning model, we will evaluate multiple types of architectures, including logistic regression, random forests, gradient boosted machines, extreme gradient boosting, neural networks, and ensemble models. Hyperparameters will be tuned using the validation cohort and models iteratively trained until a final candidate model is identified. This model will then be evaluated on the held-out internal test set and the external test cohort, after which no further model training will be performed. These steps will be performed separately for the ePRO-responding cohort and the total cohort.

To develop clinical risk scores, we will select approximately 20 independent variables that can be easily abstracted from a patient's medical chart, such as diagnosis, treatment, comorbid conditions, recent hospitalizations, and demographics. Within the training cohort, we plan to use logistic regression with L1 regularization to select variables for inclusion and define the prediction model. The amount of regularization will be tuned using the validation cohort and models will be iteratively trained until a final candidate model is identified. Like above, these steps will be completed separately for the ePRO-responding and total cohorts. The area under the receiver operator characteristic curve (AUC-ROC) will be used to compare the performance (i.e., predictive ability) of different models.

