**Defining and operationalizing the denominator:**

- To determine if a patient has a diagnosis of one of the priority cancer types, use ICD-10 diagnosis codes: 15.0-16.99 (esophago-gastric) C17.0-C21.9 (small int. colorectal) C22.0-24.9 (hepatobiliary) C23-C25.9 (pancreas), C34-34.9: lung, C53.0-53.9 (cervix) C54-54.9 (uterine) and/or C56-57.9 (ovarian). When it comes time to execute, this list may be modified. CPT and procedure codes as well as EPIC operating room scheduling lists will be used to determine if a patient is scheduled for a priority surgery.
- Participants assigned to eSyM+ may be trained to use eSyM by their local clinic/study staff. Surgical patients may be trained to use eSyM at the time of surgical discharge (or at the site's discretion patients may receive training in how to use eSyM at a preoperative visit). Med Onc patients may be trained to use eSyM at the time of their first chemotherapy dose visit or at the time of a pre-treatment visit for chemotherapy teaching (at the site's discretion). Epic reports may also be used to identify eligible patients who are assigned or will be assigned to eSyM so that training of the eligible patients can be done by study research staff via telephone or email before or after beginning treatment or having surgery.
- Participants in the eSyM- cohort will meet priority population criteria and be seen at a participating site between 1/1/2018 and the site's eSyM go-live date. Participants in the eSyM+ cohort will meet priority population criteria and be seen at a participating site after their eSyM go-live date through March 31, 2024.

**Mode of Participation:** Patients will have a *choice* of their preferred mode of eSyM participation and switching can be accommodated. Patients with a smart phone will be offered that approach first, however all patients will be notified that access to eSyM is available as long as they can access the secure patient portal (MyChart). eSyM can be accessed securely through the MyChart portal on any web-enabled device. Alternatives to smart phone reporting include

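### Activity 5 puts models with ePROs in survey responders and models without ePROs in all patients, so it specifies no like-for-like test of whether ePROs improve prediction

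*Protocol*

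**What the plan says.** The protocol poses the question twice. In section 5.0, Activity 5, the Specific Aims include "Assess whether inclusion of ePROs improves algorithm performance", and the activity description lists "how ePRO data affect model performance" among the questions to be addressed.

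Section 10.0, Analysis of Activity 5, then ties the predictor set to the cohort:

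- With ePROs: "For models incorporating ePROs as predictors, the analytic cohort will include patients who completed at least one survey".
- Without ePROs: "For models excluding ePROs as predictors, the analytic cohort will include all patients in the database".

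The database is broad: "All patient-level data collected in Activity 4 will be utilized". Under Activity 4, the eSyM- cohort is defined as patients who meet the priority criteria and "be seen at a participating site between 1/1/2018 and" the site's go-live date.

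The same analysis section holds out at least one health system as an external test set. It splits the remaining patients 70/15/15 and says that one set of cohorts serves every algorithm. Machine-learning development is run separately in the responding cohort and the total cohort, and so is the clinical risk score of about 20 chart variables. AUC-ROC "will be used to compare the performance (i.e., predictive ability) of different models".

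**The concern.** To learn what ePROs add, one compares a model with them and a model without them in the same patients. The cohort rule gives the two predictor sets different patients. Reading a survey here as the eSyM symptom survey, every responder was treated after go-live and exposed to eSyM. The total cohort adds eSyM- patients back to 2018, who had no such survey to complete, and eSyM+ patients who never responded.

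The SAP itself treats these groups as different. Section 4.2 and Table 7 model engagement on age, race, employment, insurance, cancer type, comorbidity and other variables before engaged episodes are compared with others. Section 4.7 hypothesises that eSyM lowers 30-day ED treat-and-release by 3 to 4 percentage points. Section 3.6 reports fewer ER events than expected at three sites because of COVID. Exposure and calendar period may therefore affect an outcome that Activity 5 wants to predict.

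At stake is the answer to Aim 2: useful ePROs could appear to lower AUC, and uninformative ones could appear to raise it.

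**Working it through.** The documents give no AUC, sample size or power for Activity 5, so there is no figure to reproduce. The check has two parts.

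**1. Which models exist in which cohort, as written**

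| Model | Responders | All patients |
|---|---|---|
| Machine learning with ePROs | yes | no |
| Machine learning without ePROs | not specified | yes |
| Clinical risk score (example variables name no ePROs) | yes | yes |

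The cell needed for a like-for-like machine-learning comparison is the one not specified.

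**2. What a cross-cohort contrast would measure**

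Let A(with, R) be the AUC with ePROs in responders, A(without, R) the AUC without ePROs in responders, and A(without, all) the AUC without ePROs in all patients. Then, as an identity:

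A(with, R) − A(without, all) = [A(with, R) − A(without, R)] + [A(without, R) − A(without, all)]

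The first bracket is the ePRO gain. The second is the error. It involves no ePROs, and in general it vanishes only if the chart-only model discriminates equally well in both groups.

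*Simulation A.* Assumed: event rate 10%; log-odds = constant + chart risk + ePRO part, both normal; 2,000,000 patients per scenario.

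- Chart-risk SD 1.0 in all patients and 0.8 in responders, ePRO SD 0.4. A(without, all) = 0.747, A(without, R) = 0.705, A(with, R) = 0.728. Cross-cohort contrast 0.728 − 0.747 = −0.019; true gain 0.728 − 0.705 = +0.023; error 0.705 − 0.747 = −0.042.
- Chart-risk SD 1.0 in all patients and 1.2 in responders, ePROs uninformative. Contrast 0.785 − 0.750 = +0.035; true gain 0; error +0.035.

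Numerical integration of the same model reproduces all five AUCs to within 0.001.

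*Simulation B.* Assumed: event rate 12%; chart-risk SD 1.0; 30% or 50% of patients respond; the log-odds of responding fall by 0, 1 or 2 per SD of risk; ePRO log-odds effect 0, 0.3 or 0.5 per SD; 1,000,000 patients per scenario. Each cell shows the cross-cohort contrast, then the true gain in responders.

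| ePRO effect | No selection | Moderate (1) | Strong (2) |
|---|---|---|---|
| 0 | 0.000; 0.000 | −0.012 to −0.015; 0.000 | −0.044 to −0.046; 0.000 |
| 0.3 | +0.012; 0.010 to 0.011 | −0.003 to −0.005; 0.011 to 0.012 | −0.031; 0.012 to 0.013 |
| 0.5 | +0.028; 0.027 | +0.016 to +0.018; 0.029 to 0.031 | −0.006 to −0.007; 0.035 to 0.037 |

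Subtracting the gain from the contrast, scenario by scenario, gives an error of at most 0.002 with no selection. It is −0.012 to −0.016 with moderate selection and −0.042 to −0.046 with strong selection. For example, at effect 0.3 with strong selection and 30% responding, −0.031 − 0.012 = −0.043.

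**The case against.** Four points can be made for the plan.

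- **A model without ePROs may exist in responders.** The clinical risk score is run in both cohorts, and its example variables are all chart items. A reader might infer that no model without ePROs is planned in responders at all; the text does not support so flat a statement. But this reading conflicts with the rule that models without ePROs use all patients. Setting that score against a machine-learning model with ePROs also changes model type and predictors together, so the ePRO contribution is still not isolated.
- **The cross-cohort contrast is not stated.** A reader might infer that the protocol commits to it. The AUC sentence speaks only of different models, and it closes the paragraph on risk scores. It could refer to risk scores versus machine learning, or to comparisons within each cohort. This stands: the contrast is what the cohort rule leaves for Aim 2, not a declared analysis.
- **The right comparison remains possible.** If the split is shared, responders in the test sets are a subset of the all-patient test sets, and the all-patient model could be scored on them. So it is too strong to say that Activity 5 cannot answer Aim 2. Equally, the statement that one set of cohorts serves all algorithms does not promise such scoring, and it does not displace the explicit cohort rule.
- **The magnitudes are assumed.** The risk spreads, event rates and response patterns are not in the documents. With no selection the contrast is nearly right. The simulations show that error is possible in either direction, not how large it is here. Nor are responders necessarily active portal users acting for themselves, since Activity 4 allows completion in clinic and by proxy.

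**Conclusion.** The point holds as a gap in the plan as written. The cohort rule is explicit, and under it Aim 2 has no like-for-like machine-learning comparison. A contrast across the two cohorts would combine ePRO value with case-mix, calendar period and eSyM exposure.

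The direction and size of the error cannot be known from the documents. Under the assumptions above it runs from about −0.046 to +0.035 AUC, which can exceed the gain being sought (0.010 to 0.037 where ePROs were informative in these simulations). It is almost nil if responders share the risk mix of all patients, a condition that the plan neither states nor checks.

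Activity 5 is a retrospective prediction project using Activity 4 data. Nothing here touches the Activity 4 analyses.

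**What to change.** Amend section 10.0, Analysis of Activity 5, as follows:

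1. In the ePRO-responding cohort, fit each architecture and the clinical risk score with and without ePRO predictors, on the same patient-level split and the same external site.
2. Report the paired AUC difference with a 95% interval on the same test patients, as the answer to Specific Aim 2.
3. Keep the all-patient model without ePROs as a separate result, and state that it is not used to judge the value of ePROs.
4. Reconcile the cohort rule with the paragraph that runs the clinical risk score in both cohorts, and say whether that score may contain ePROs.

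The cost is protocol wording and extra model runs on data already collected. The limitation is that the Aim 2 result then applies to responders only, which should be stated when it is reported.
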